5.4.5.3 Cycles 2 - 4, Day 1 – Dosing

- Treatment with **ACM** or **CM**.
After completing the first cycle of treatment, continued use of mitoxantrone is optional.
- Collect blood for evaluation of laboratory parameters (*Appendix D*):
 - Hematology
 - Tumor lysis labs
 - Fibrinogen level (only required if clinically indicated)
- If supportive care measures for prevention of tumor lysis were initiated, monitor urine output **frequently** to ensure that it equals fluid input. If input is greater than output by 10%, administration of diuretics is encouraged. Replacement of excessive fluid losses, including from diarrhea, should be done unless otherwise clinically indicated.
- Test for presence of *C. difficile* infection at first instance of diarrhea (refer to *Section 4.6.1.2* for additional guidance)
- Administer prophylactic antibiotics and antivirals, corticosteroid eye drops, and antifungals according to *Section 4.6.1.4*.
- Assess for AEs
- Record only those medications (prescription, nonprescription, nutritional supplements) administered in conjunction with an AE.

5.4.5.4 Cycles 2 - 4 – Daily during Hospitalization for Chemotherapy

Perform the following procedures daily (or more frequently if clinically indicated) while patients are hospitalized for chemotherapy administration:

- Collect blood for evaluation of laboratory parameters (*Appendix D*):
 - Hematology
 - Tumor lysis labs
 - Fibrinogen level (only required if clinically indicated)

- If supportive care measures to prevent/treat tumor lysis were initiated, must monitor urine output **frequently** to ensure that it equals fluid input. If input is greater than output by 10%, administration of diuretics is encouraged. Replacement of excessive fluid losses, including from diarrhea, should be done unless otherwise clinically indicated.
- Test for presence of *C. difficile* infection at first instance of diarrhea (refer to *Section 4.6.1.2* for additional guidance)
- Assess for AEs
- Record only those medications (prescription, nonprescription, nutritional supplements) administered in conjunction with an AE.

5.4.5.5 Cycles 2 - 4 – Weekly after Completion of Chemotherapy Regimen

Perform the following procedures weekly (or more frequently if clinically indicated) after patients have completed their chemotherapy regimen:

- Abbreviated physical examination including weight (kg)
- Vital signs (temperature, heart rate, systolic and diastolic blood pressures)
- Assess ECOG PS (*Appendix B*)
- Collect blood for evaluation of laboratory parameters (*Appendix D*):
 - Hematology
 - Tumor lysis labs
 - Fibrinogen level (only required if clinically indicated)
- Assess for AEs
- Record only those medications (prescription, nonprescription, nutritional supplements) administered in conjunction with an AE.

5.4.5.6 Cycles 2 - 4 – At Hematologic Recovery

- Assess response by bone marrow biopsy and/or aspiration at time of hematologic recovery (ie, absolute neutrophil count (ANC) >1000 μ L and platelet count >100,000 μ L) or Day 45 (\pm 2), whichever occurs first. If the bone marrow biopsy and/or aspirate is nonproductive or not diagnostic, the procedure must be repeated within 7 days.
 - At time of response assessment, 6 to 8 bone marrow slides will be prepared and sent to the Sponsor. Details regarding the collection and shipping of these slides is provided in the Study Manual.
- Assess for AEs, including tumor lysis clinical symptoms

- Record only those medications (prescription, nonprescription, nutritional supplements) administered in conjunction with an AE.

5.5 End of Study Assessments (Stage 1, Stage 2)

To be completed at time patient is withdrawn from the study.

- Abbreviated physical examination including weight (kg) and other measures of disease and disease symptoms, eg, extramedullary disease
- Vital signs (temperature, heart rate, systolic and diastolic blood pressures)
- ECOG PS (Appendix B)
- Collect blood for evaluation of laboratory studies (Appendix D):
 - Hematology
 - Full serum chemistry panel
 - Fibrinogen level (only required if clinically indicated)
- Urinalysis
- Perform bone marrow biopsy and/or aspiration (if not done in the preceding 30 days). If the bone marrow biopsy and/or aspirate is nonproductive or not diagnostic, the procedure must be repeated.
 - At end of study, 6 to 8 bone marrow slides will be prepared and sent to the Sponsor (if not done in the preceding 30 days). Details regarding the collection and shipping of these slides is provided in the Study Manual.
- Perform 12-lead ECG (as clinically indicated)
- Perform ECHO or MUGA scan (as clinically indicated)
- Assess for AEs
- Record only those medications (prescription, nonprescription, nutritional supplements) administered in conjunction with an AE

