4.5.3.2 Stage 2: Treatment with ACM or CM

Patients enrolled in Stage 2 will be randomized to either ACM or CM and will receive treatment as outlined below:

Stage 2: Randomized to ACM: Treatment with ACM over Days 1-9

Follow the Stage 1 treatment schema above

Stage 2: Randomized to CM: Treatment with CM over Days 1-4

- **Days 1, 2, and 3: cytarabine (C) - Continuous over 72 hours**
2 gm/m² by continuous IV infusion over 72 hours (± 2.5 hours)
(ie, 667 mg/m² daily for total of 2 gm/m²)
- **Day 4: mitoxantrone hydrochloride (M) is administered 12 hours after completion of cytarabine treatment**
40 mg/m² by IV infusion over 1-2 hours (± 10 minutes)

4.5.3.3 Evaluation After Cycle 1

- Patients who achieve CR, CRi, CRp, or PR after the first cycle (completion of all doses) may receive up to 3 additional optional cycles of treatment.
 - After completing the first cycle of treatment, continued use of mitoxantrone is optional.
 - Mitoxantrone must be omitted from subsequent cycles if the patient's lifetime daunorubicin equivalent exceeds 460 mg/m² (see *Appendix G* for conversion table) or the left ventricular ejection fraction (LVEF) drops below 45%.
- Patients not demonstrating evidence of CR, CRi, CRp, or PR after the first cycle of treatment will be considered for removal from the study, although with permission of the Medical Monitor, induction treatment may continue if clinically indicated and provided there is no evidence of toxicity \geq NCI CTCAE grade 4.
- Perform the End of Study Assessments for those patients who do not continue on study to receive at least one additional cycle of treatment (see *Section 5.5*).

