5.6 Follow-up Assessments (Stage 1, Stage 2 and Exploratory Arms)

All study patients will be contacted by telephone to assess for date of death, date of stem cell transplant, date of relapse, or continued remission for two years:

- Year 1: Phone calls monthly beginning the month after the patient completes the end-of-study assessments to 12 months after Day of Randomization regardless of how many cycles a patient receives (Year 1 = Day of Randomization plus 12 months)
- Year 2: Phone calls every other month during Year 2 (months 14 to 24 after Day of Randomization).

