6. OFF-STUDY CRITERIA

6.1 Withdrawal of Patients

All patients have the right to withdraw at any time during treatment without prejudice. Circumstances may occur under which a patient may be permanently removed from the study. The criteria used to justify withdrawal of a study patient are described below.

In the event of a premature withdrawal, the assessments for the End of Study visit, as detailed in the Schedule of Activities (See [Appendix A](#)), should be completed at the time of the withdrawal, wherever possible, including dates of remission and death. If the study patient is prematurely withdrawn due to an adverse event(s), attempts should also be made to clinically follow the study patient until the event is resolved, stable or permanent as determined by the PI and Sponsor.

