6.3 Follow-up for Patients Withdrawn from Study

Patients withdrawn from the study with an ongoing adverse event must be followed clinically until the event is resolved, deemed stable or permanent by the PI, or the patient begins a new treatment for their disease. A stable adverse event is defined as an event that is not expected to change in nature, severity or frequency. See Sections 8.4 – 8.8 for reporting of adverse events. Patients withdrawn from the study for pregnancy will be followed according to Section 5.6 Follow-up Assessments. The pregnancy of any patient, or patient's partner, will be followed to term to record any birth defects/abnormalities at time of birth.

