8.3 Serious Adverse Events

A serious adverse event (SAE) is defined as any experience that suggests a significant hazard, contraindication, side effect, or precaution. An SAE includes:

- Any death, or
- Any life-threatening event (ie, the patient is at immediate risk of death from the event as it occurred), or
- Any event that is persistently, significantly, severely or permanently disabling, or requires intervention to prevent such disability, or
- Any event which requires inpatient hospitalization or prolongs hospitalization, or
- Any congenital abnormality/birth defect, or
- Any medically significant event that may jeopardize the patient or may require intervention to prevent one of the other outcomes listed above.

In addition, any adverse event which results in termination of the patient from study will be considered a potentially serious adverse event and must be reported to the Sponsor as described in Section 8.4 below.

Bone marrow suppression and associated complications are expected events during leukemia therapy and are part of the treatment process (marrow emptying of leukemic cells). Therefore, myelosuppression and associated complications directly related to the myelosuppression, such as fever, infections and bleeding, will not be reported as serious adverse events (SAEs), but will be reported as adverse events on the adverse event CRF and will be summarized in the updated and final reports. Anemia and thrombocytopenia will not be reported as an SAE. Prolonged bone marrow suppression (as defined by the NCI toxicity criteria specific for leukemia, ie, bone marrow cellularity <5% on day 42 or later (6 weeks) from start of therapy without evidence of leukemia) or the unexpected nature, severity or frequency of myelosuppression, anemia, and thrombocytopenia or an associated complication will be reported as an SAE.

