11.4.4 Safety Analyses

The following safety analyses will be performed on all patients who receive at least one dose of study drug.

- **30- and 60-day Mortality** = Estimates of 30- and 60-day mortality and their pointwise 95% CIs will be derived from Kaplan-Meier curves for OS by treatment arm
- **Adverse Events** = Reported AE terms will be mapped to MedDRA preferred terminology. All reported events will appear in AE listings, however only TEAEs will be summarized. A TEAE is an AE that starts or increases in severity any time after the first administration of any study drug up to 30 days following the last administration of any study drug. AE severity will be rated by the investigator according to NCI CTCAE version 4.03 in Stage 1 and version 5.0 in Stage 2 (see *Appendix C*).
- **Clinical Laboratory Assessments** = Laboratory test results measured on a continuous scale and changes from baseline values will be summarized by visit and within treatment arm using mean, standard deviation, median, minimum and maximum values. Categorical test results will be summarized within treatment arm using shift tables. Additionally, for tests where NCI CTCAE, version 4.03 in Stage 1 and version 5.0 in Stage 2 (see *Appendix C*), severity criteria are specified, NCI CTCAE severity grades will be summarized in shift tables.
- **Vital Signs** = Vital signs and changes from baseline values will be summarized by visit and within treatment arm using mean, standard deviation, median, minimum and maximum values.

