7.11.2. Adverse Events

Reported adverse event (AE) terms will be mapped to MedDRA preferred terminology. AEs suggestive of tumor lysis syndrome (TLS) will be flagged based in the standardized MedDRA query (SMQ) for TLS. All reported events will appear in AE listings, however only treatment-emergent adverse events will be summarized. A treatment-emergent adverse event (TEAE) is an AE that starts or increases in severity any time after the first administration of any study drug up to 30 days following the last administration of any study drug. AE severity was rated by the investigator according to Common Terminology Criteria for Adverse Events (CTCAE) version 4.03 criteria.¹³

A high-level safety summary will display the numbers of patients within each treatment arm and overall who experience one or more AEs in each of the following categories:

- All TEAEs regardless of severity or presumed relationship to study drug
- TEAEs judged related to study drug
- All TLS SMQ TEAEs
- TLS SMQ TEAEs judged related to study drug
- Treatment-emergent serious adverse events (SAEs)
- TEAEs leading to a delay in the administration of study drug
- TEAEs leading to a reduction in the protocol-specified dose of study drug
- TEAEs leading to discontinuation of study drug
- TEAEs leading to withdrawal from the study
- TEAEs leading to death

The base summary of TEAEs will show within- and between-treatment-arm incidence rates for each MedDRA primary SOC and/or PT by highest reported CTCAE severity grade and overall. A separate summary will be produced each of the AE subsets listed above. Additional AE summaries may be produced using safety data from subsets of patients and/or characterized using additional SMQs.

Partial start and end dates for adverse events will be replaced by calendar dates that maximize the duration of the adverse event. The following steps will be followed.

For a partial start date:

1. Replace a missing month with January
2. Replace a missing calendar day with the first of the month
3. If the replacement date is prior to the first dose of study drug, then set the adverse event start date equal to the date of the first dose

For a partial end date:

1. Replace a missing month with December
2. Replace a missing calendar day with the last day of the month

The replacement date for a missing end date may exceed end of the adverse event reporting period specified in the study protocol.

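### The last scheduled adverse-event question is at End of Study, which can come before the 30-day treatment-emergent window closes; later events other than serious or unexpected severe ones then rely on passive capture

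*Protocol*

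**What the plan says.** **Counting window.** Protocol 11.4.4 treats as treatment-emergent any adverse event (AE) that begins or worsens after the first dose, "up to 30 days following the last administration of any study drug". SAP 7.11.2 sets the same limits: "any time after the first administration of any study drug up to 30 days following the last administration of any study drug". Neither restricts the count to drug-related events.

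**Last scheduled question.** AEs are assessed at dosing, daily in hospital, weekly after chemotherapy, at the response marrow and at End of Study (Protocol 5.3 to 5.5). On the timing of End of Study, 5.5 says: "To be completed at time patient is withdrawn from the study". Protocol 4.5.3.3 gives a second trigger: "Perform the End of Study Assessments for those patients who do not continue on study to receive at least one additional cycle of treatment". Protocol 6.1 adds: "All patients have the right to withdraw at any time during treatment without prejudice". No section sets a minimum interval between the last dose and this visit.

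**Follow-up calls.** Protocol 5.6: "All study patients will be contacted by telephone to assess for date of death, date of stem cell transplant, date of relapse, or continued remission". AEs are not on that list. The follow-up footnotes in Appendix A repeat the same items.

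**What still applies after the visit.**
- Protocol 8.4 records AEs that staff notice or patients volunteer, with no end date. It also asks for unexpected Grade 3 or higher AEs to be reported for 30 days after study drug, or until alternate cancer therapy if that is earlier.
- Protocol 8.5 sets a similar 30-day duty for serious AEs (SAEs), with the same cut-off.
- Protocol 8.3 says that complications of myelosuppression, "such as fever, infections and bleeding, will not be reported as serious adverse events"; they go on the AE form instead. Complications unexpected in nature, severity or frequency remain SAEs.
- Protocol 8.6 sends events that patients report after the last scheduled visit to the sponsor if they are judged drug-associated or are otherwise reportable.
- Protocol 6.3 covers events already under way: "Patients withdrawn from the study with an ongoing adverse event must be followed clinically until the event is resolved", or until it is stable or permanent, or new treatment starts.

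**The concern.** The reporting window and the asking window are set by different clocks. The first runs from the last dose. The second stops when the patient leaves the study.

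The SAP table templates show TEAEs as numbers and percentages of patients, with no allowance for how long each patient was asked. A day inside the window on which nobody asks is in effect counted as event-free.

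The events most exposed matter in this setting. Protocol 8.3 regards fever, infection and bleeding from myelosuppression as expected and takes them out of SAE reporting, so after End of Study they have no active route. The 8.6 route also applies a relatedness or reportability test, in an open-label trial, to events that feed tables meant to include every AE.

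Finally, SAP 7.11.2 refers to an AE reporting period specified in the protocol. Protocol 8.4 gives a start for AEs in general but no end. What is at stake is the completeness of the TEAE rates. The primary endpoint is not affected.

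**Working it through.** The plan states no figure for this gap, so there is none to reproduce. The check is day arithmetic.

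**Inputs**
- Window length: 30 days after the last dose (Protocol 11.4.4, SAP 7.11.2).
- Last dose in a full cycle: Day 9 for ACM (Protocol 4.5.3.1), Day 4 for CM (4.5.3.2).
- Response marrow: hematologic recovery or Day 45 (±2), whichever is first (5.3.4, 5.4.4).
- Day of the End of Study visit: not given. The days below are assumptions that show the range.

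**Step 1: window end** = last dose day + 30.
- ACM: 9 + 30 = Day 39.
- CM: 4 + 30 = Day 34.

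**Step 2: gap** = max(0, window end − End of Study day), with the visit on the same cycle day in both arms.

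| End of Study (assumed) | ACM gap | CM gap |
|---|---|---|
| Day 15 | 39 − 15 = 24 days (24/39 = 62%) | 34 − 15 = 19 days (19/34 = 56%) |
| Day 21 | 18 | 13 |
| Day 30 | 9 (9/39 = 23%) | 4 (4/34 = 12%) |
| Day 35 | 4 | 0 |
| Day 39 or later, including Days 43 to 47 | 0 | 0 |

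If mitoxantrone is omitted, the last doses fall on Days 8 and 3, the windows end on Days 38 and 33, and a Day 30 visit leaves 8 and 3 days.

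**Step 3: the same visit placed k days after the last dose.** The gap is 30 − k in either arm: 10 and 10 days for k = 20, 5 and 5 for k = 25. The difference between arms in Step 2 therefore comes entirely from assuming the same cycle day.

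**Step 4: what is exposed inside the gap.**

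| Event type | Route after End of Study |
|---|---|
| SAE | Active duty to 30 days or alternate cancer therapy (8.5) |
| Unexpected, Grade 3 or higher | Active duty, same limits (8.4) |
| Myelosuppression complication unexpected in nature, severity or frequency | SAE route (8.3, 8.5) |
| Expected fever, infection or bleeding from myelosuppression | Noted or volunteered only (8.4, 8.6) |
| Other non-serious AE, expected or below Grade 3 | Noted or volunteered only (8.4, 8.6) |

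The two active duties can end inside the TEAE window if alternate cancer therapy starts. The TEAE definition has no such cut-off.

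**The case against.** The best defence is that collection does not stop at End of Study. Protocol 8.4 records noted or volunteered AEs at any time, with no relatedness test. SAEs and unexpected Grade 3 or higher AEs have a dated duty. Protocol 8.7 requires an SAE report for a death within 30 days of the last dose. Patients withdrawn with an ongoing AE are still followed clinically, so staff may notice new events. Patients who have not recovered and stay until the Day 45 marrow are seen after both windows have closed. No passage says how many patients leave before Day 39 or Day 34.

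All of this stands, and it limits the point. A reader might infer that late TEAEs in general are lost; the documents do not support that. What survives is narrower: for the last two rows of Step 4, capture in the gap is passive.

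A reader might also infer that ACM loses more events and so looks safer than it is. That does not follow, for three reasons.
- The five-day difference needs the visit on the same cycle day in both arms. If recovery is timed from the end of cytarabine and mitoxantrone, Step 3 gives equal gaps. The documents give no recovery times or visit dates by arm.
- CM non-responders may cross over and keep scheduled AE assessments, but crossover is optional. ACM non-responders are only considered for removal and may continue with the Medical Monitor's permission (4.5.3.3, 4.5.3.4).
- Protocol 11.3 counts any patient given alvocidib as ACM for safety, while SAP 7.1 excepts crossover patients. The arm credited with their longer observation depends on which rule is used.

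Nor do the documents show that the loss is greatest in patients withdrawn for toxicity, since those patients have mandated follow-up of the event.

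**Conclusion.** The gap is real but limited. Followed as written, the plan can leave part of the 30-day TEAE window with no scheduled AE question whenever End of Study falls before Day 39 (full ACM cycle) or Day 34 (full CM cycle). The exposed events are expected complications of myelosuppression and non-serious AEs that are expected or below Grade 3. TEAE rates for these may be under-ascertained.

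The gap is 0 days for a Cycle 1 visit at Day 45, 9 (ACM) or 4 (CM) days for an assumed Day 30 visit, and 24 or 19 days for an assumed Day 15 visit. These describe single hypothetical patients. The effect on arm-level rates cannot be computed without the distribution of visit days. Observation time may differ by arm, but its size and direction cannot be derived from the documents.

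This is worth correcting because the correction is cheap. It is not evidence of bias towards either arm.

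**What to change.** In Protocol 5.5, 5.6, 8.4 and Appendix A, state that all AEs, and the medications given for them, are collected to 30 days after the last dose of study drug in every patient. If End of Study is earlier, ask at the first scheduled monthly call about new AEs, with onset dates, and enter those that began inside the window.

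That call should normally be late enough. Protocol 5.6 starts the calls the month after End of Study. If this means about 30 days later (an assumption), the call falls on or after last dose + 30, because End of Study cannot precede the last dose. For a Day 15 visit it would be Day 45, after both windows have closed. If a site calls sooner, the question should be repeated at the next call.

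The cost is protocol and case report form wording, a few questions in an existing call, and slightly more data entry. No visit is added. The weakness is reliance on recall by telephone, which is less exact than a clinic assessment but better than no question.

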5.6 Follow-up Assessments (Stage 1, Stage 2 and Exploratory Arms)

All study patients will be contacted by telephone to assess for date of death, date of stem cell transplant, date of relapse, or continued remission for two years:

- Year 1: Phone calls monthly beginning the month after the patient completes the end-of-study assessments to 12 months after Day of Randomization regardless of how many cycles a patient receives (Year 1 = Day of Randomization plus 12 months)
- Year 2: Phone calls every other month during Year 2 (months 14 to 24 after Day of Randomization).

